6.3 Statistical criteria of termination of the investigation

The study will be terminated if more than 20% of the restorations fail (FDI grade 5 on any of the criteria).

The study would be terminated prior to reaching baseline if more than 5 treated teeth were found to have post-operative hypersensitivity (FDI 11 >grade 3).

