MedDO	Medical Devices Ordinance (in German: MepV, in French: Odim, in Italian: Odmed)
MD	Medical Device
MDR	Medical Device Regulation (EU) 2017/745 of 5 April 2017
PI	Principal Investigator
SADE	Serious Adverse Device Effect
SAE	Serious Adverse Event
SDV	Source Data Verification
SNCTP	Swiss National Clinical Trials Portal
SOP	Standard Operating Procedure
USADE	Unanticipated Serious Adverse Device Effect

INVESTIGATION SCHEDULE

Study Periods	Screening	Treatment, Intervention Period				Follow-up						
		1	2	3	4***	5	6	7	8	9	10	11
Visit	1											
Time (hour, day, week)	-17- (-45) d	-14- (-5) d	0 d	Before visit 5	6-12 d	1 m	6 m	12 m	24 m	36 m	60 m	
Patient Information	x											
Signed informed consent		x										
Medical History	x											
In- /Exclusion Criteria	(x)	x										
Tooth Examination	x											
Pregnancy Test		x										
Vitality test	x	x			x	x	x	x	x	x	x	x
VAS for tooth sensitivity		x			x	x	x	x*	x*	x*	x*	x*
Preparation of tooth, impression and cementation of provisional restoration		x										
Try-in and cementation of final restoration			x									
Use of [REDACTED]			x									
Excess removal, polishing, occlusion check			x	x								
Primary Variables					x	x	x	x	x	x	x	x
Secondary Variables					x	x**	x	x	x	x	x	x
Photographs		x	x		x	x	x	x	x	x	x	x
Adverse events and device deficiencies		x	x	x	x	x	x	x	x	x	x	x

* only for participants who suffer from any kind of postoperative hypersensitivity

** Not all variables will be assessed (only dental hard tissue defects at restoration margin, patient's view and fracture of material and retention)

*** optional visit

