3. CLINICAL INVESTIGATION OUTCOMES

3.1 Primary Outcome

Postoperative hypersensitivity is considered an indicator of the response of a tooth (pulp) to the therapeutic procedure applied. Postoperative hypersensitivity can be observed within a short time after the treatment. Therefore, it is assessed for the first time at the baseline recall (after 6-12days). The assessment of postoperative hypersensitivity includes questions about type and duration of pain, intensity of pain and on the stimulus inducing the pain (Hickel et al. 2007, Hickel et al. 2010, Hickel et al. 2022). The subjective perception of the intensity of postoperative hypersensitivity caused by thermal stimuli and caused by occlusal forces (during biting) will be determined by the aid of a Visual Analog Scale (VAS). The VAS values are brought into relationship to the preoperative values. In the table below a description of the correlation between FDI grade and VAS values and clinical signs and symptoms is shown. Not all signs need to be present at one stage. The exact VAS values vary widely from patient to patient, depending on each individual's pain tolerance. Therefore, it is one of the factors influencing the FDI grade, but it is not directly correlated. Not all the described conditions have to be fulfilled to attribute an FDI score. Depending on the intensity and character of the pain, further therapy will be determined. Usually, postoperative hypersensitivity subsides spontaneously, and no treatment is necessary. In case of very intense pain an immediate treatment is required. The application of a fluoride varnish is the first procedure of choice. If no improvement is achieved by this method, then the replacement of the restoration would be the next step. In the worst case, the pulp is severely inflamed, requiring endodontic treatment. If the postoperative hypersensitivity does not subside spontaneously or worsens after the applied treatment, the highest assessed FDI value is used for the statistical analysis.

For all participants a 1-month recall is planned to finally assess the postoperative hypersensitivity. The clinical experience of the evaluator is of major importance in the correct assessment of the FDI grade. In general, the rule applies, that in case of uncertainties the higher score is attributed.

FDI grade	1	2	3	4	5

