4.1 General clinical investigation design and justification of design

████████ a new dental adhesive will be used to lute 45 inlays or onlays out of e.max CAD to teeth of at least 23 patients.

This prospective study has only one group (████████) because the planned study is similar to a trial which has recently been executed in the internal clinic of Ivoclar Vivadent AG (NCT04475679). The only difference to the already performed study is the device under assessment. Therefore, the coded results of the control group of the previous clinical investigation (Adhese Universal) will be compared with the clinical performance of the new dental adhesive (████████).

There are 5 operators and 2 evaluators. All operators are very experienced dentists in the field of restorative dentistry. The treatment of restoring teeth with ceramic inlays or onlays is a standard treatment in the internal clinic of Ivoclar Vivadent AG.

Postoperative sensitivities arise within days after the treatment. Therefore, the occurrence of postoperative sensitivities can be assessed already at baseline. Final assessment of postoperative hypersensitivities will be performed at the 1-month recall. If such an incident is still present after 1 month, it will be followed regularly.

The study duration of 5 years corresponds to the minimal duration recommended in restorative dentistry (Hickel et al., 2022). The patients will attend a recall after 6-12 days (baseline), 1, 6, 12, 24, 36, and 60 months.

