6.4.2 Primary Analysis

Regarding the primary outcome, the interim analysis will be done at baseline. The final analysis of the primary outcome will be done after completion of the 1-month recall. The analysis will be done by the principal investigator within 3 months after the collection of the 1-month data.

A non-parametric test (Mann-Whitney) between two independent groups will be used to compare the level of postoperative hypersensitivity (FDI 11) between the control and the test group.

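### The hypersensitivity stopping rule in 6.3 is tied to a period in which no count is stated, and a sentence in 6.4.4 contradicts the 20% failure rule (minor, wrong as written)

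*Combined protocol and SAP*

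**What the plan says.** Section 6.3 sets two termination criteria.

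- Failure: "The study will be terminated if more than 20% of the restorations fail (FDI grade 5 on any of the criteria". No time limit, look or denominator is attached.
- Hypersensitivity: "The study would be terminated prior to reaching baseline if more than 5 treated teeth were found to have post-operative hypersensitivity", with the cut-off at FDI 11 above grade 3.

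On when hypersensitivity is graded, section 3.1 says: "Therefore, it is assessed for the first time at the baseline recall (after 6-12days". Section 4.1 adds: "Final assessment of postoperative hypersensitivities will be performed at the 1-month recall", and "If such an incident is still present after 1 month, it will be followed regularly". In the investigation schedule the only contact between luting and the baseline recall is visit 4, footnoted as "optional visit". Section 3.1 also provides for urgent cases: "In case of very intense pain an immediate treatment is required".

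On when the data are examined, section 6.4.2 says: "Regarding the primary outcome, the interim analysis will be done at baseline", with the final analysis after the 1-month recall. Section 6.4.4 lists interims at 6, 12, 24, 36 and 60 months. It then says that stopping guidelines are not needed because the restorations are final interventions. Its next paragraph justifies the absence of any adjustment by saying that the interims exist for safety stopping alone.

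Section 6.5 speaks of the completion of all baseline examinations as the point after which drop-outs are not replaced.

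**The concern.** A rule that limits exposure to a device without conformity marking has to be countable while teeth are still being luted. Section 6.3 gives the rule a window that closes at baseline. Baseline is also when the outcome is first scheduled to be graded and when the only early look takes place. Section 6.3 does not say whether baseline means each tooth's own recall or the completion of all baseline recalls, and it does not say that cases are tallied as they occur. Followed to the letter on one reading, the rule has almost nothing to count.

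The second problem is a contradiction. Section 6.3 orders termination above 20% failures without a time limit. Section 6.4.4 says that no stopping guideline is needed, then gives safety stopping as the sole purpose of the same interims. Someone running the 12-month interim could find support for either course.

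**Working it through.** **Step 1. What the hypersensitivity window contains.**

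- *Per tooth* (luting to that tooth's day 6-12 recall): no scheduled FDI 11 grade. A case can enter only through the optional visit 4, an unscheduled visit for intense pain, or an adverse event report.
- *Per study* (first luting until all baseline examinations are done, in line with 6.5): baseline and 1-month grades of the earlier-treated teeth fall inside the window. The rule can work, provided that the count is updated as grades arrive.

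**Step 2. Thresholds.** More than 5 teeth means 6 or more, and 6/45 = 13.3%. More than 20% of 45 restorations means more than 9, so 10 or more. If only 40 remained, it would be more than 8, so 9 or more.

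**Step 3. What a running count could achieve.** The synopsis plans first subject in for October 2024 and last subject out for April 2031. Taking off 60 months of follow-up leaves October 2024 to April 2026, about 547 days. With 45 teeth evenly spaced (an assumption), 547/45 = 12.2 days per tooth. A day 6-12 grade is then known before the next tooth is luted (lag 0). A 1-month grade is known after two further lutings (lag 2).

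Let p be the true rate of grade 4-5 and treat teeth as independent. The documents give no p, so a range is shown. If the sixth case is tooth number T, the teeth spared are max(0, 45 − T − lag). Therefore:

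- expected number spared = sum over n = 0 to 44 − lag of P(Bin(n, p) ≥ 6)
- probability of sparing at least one tooth = P(Bin(44 − lag, p) ≥ 6)

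| True rate p (assumed) | Probability, lag 0 | Mean spared, lag 0 | Probability, lag 2 | Mean spared, lag 2 |
|---|---|---|---|---|
| 2% | 0.0002 | 0.00 | 0.0002 | 0.00 |
| 5% | 0.022 | 0.17 | 0.017 | 0.13 |
| 10% | 0.27 | 2.8 | 0.24 | 2.3 |
| 15% | 0.66 | 9.0 | 0.62 | 7.7 |
| 20% | 0.90 | 15.7 | 0.87 | 13.9 |

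Up to two teeth per participant are allowed. With 22 pairs and one single tooth, pairs luted together and lag 0, the mean spared at 10%, 15% and 20% is 3.3, 9.0 and 15.2 for a within-pair correlation of 0.3, and 3.7, 9.2 and 15.1 for 0.5. Clustering does not change the picture.

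**Step 4. The end of the window.** If the rule lapses once all baseline examinations are done, the last teeth lack their 1-month grade. If the last three teeth contributed nothing, the trigger probability would fall by 5.3, 6.8 and 3.8 percentage points at 10%, 15% and 20% (42 against 45 teeth). By then every tooth has been luted, so a later trigger spares nobody.

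**Step 5. Sections 6.3 and 6.4.4 side by side.** Section 6.3 says that the study will be terminated above 20% failures. Section 6.4.4 says that stopping guidelines are unnecessary, and then that the interims are only for safety stopping. The first and third statements agree; the second conflicts with both. No arithmetic is involved.

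**The case against.** The strongest reply is that 6.3 works as it stands. Baseline is most naturally the study-level milestone of 6.5, and the trigger is an absolute count. It is met when the sixth case is found and needs no scheduled analysis. At one centre staff would notice. This stands in large part: on that reading what is missing is one phrase saying that the count runs. It does not remove the ambiguity, because 6.3 leaves baseline undefined and the other reading nearly empties the window.

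A reader might infer more than the text supports, in three ways.

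- *That the rule can never fire.* It can, on the study-level reading, and through unscheduled grades on the other.
- *That all 45 teeth will be luted before anyone counts, so that none is spared.* That follows only if the count is made once, after all baseline examinations. Section 6.4.2 describes the primary-outcome interim there and does not say that the termination count waits for it.
- *That 6.4.4 cancels the hypersensitivity rule.* Its sentence sits with the 6- to 60-month interims and need not reach back to enrolment.

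It is also fair to say that grades 4 and 5 imply replacement of the restoration, endodontic treatment or both, and that section 3.1 expects hypersensitivity usually to subside untreated. The true rate may be low, and at 2% to 5% the gain is negligible. All teeth are luted by the later interims, so settling the 20% wording limits no further exposure. Finally, the sections provided contain no safety-monitoring chapter, so other suspension provisions may exist.

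**Conclusion.** The point holds as a minor one, and the text is wrong as written in two places. The 6.4.4 sentence contradicts 6.3 and the paragraph that follows it; this rests on the wording alone. The window in 6.3 is ambiguous: one reading leaves the rule no scheduled grade to count, and the other makes it work only with a running tally that is not mentioned.

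The practical size depends on an unknown rate. It ranges from almost no teeth spared at 2%, through about 0.2 at 5%, to 15.7 of 45 at 20%, assuming independent teeth, even spacing over about 18 months and cases visible at the baseline recall. These figures show what a running count can do. They are not a loss the plan is known to incur, since the plan does not exclude such a count. The lapse before the last 1-month grades has no exposure consequence. Nothing here affects the primary comparison.

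**What to change.** In 6.3, replace the restriction to the time before baseline with: *If at any time before the last restoration is luted more than 5 treated teeth have been graded FDI 11 above 3, at any scheduled or unscheduled visit, no further restorations are luted.* Add that the site keeps the running count. The sponsor's threshold and grade cut-off stay unchanged.

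In 6.4.4, delete the sentence saying that stopping guidelines are unnecessary, and state that the 6- to 60-month interims apply the 20% criterion of 6.3 (10 or more of 45 restorations).

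Optionally, extend the count to the last 1-month recall, with a crossing after the last luting leading to a safety review while follow-up continues. This spares no one and is not essential.

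The cost is a few sentences and a small tally at one site, with no extra visits, data or participants. At a true rate of 5% the running count would halt luting early with probability of only about 0.02, so the risk of stopping needlessly is low.

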6.4 Planned Analyses

The IBM SPSS Version 25 software package will be used for data analysis.

6.4.1 Datasets to be analysed, analysis populations

The data collected of all eligible participants that received a final restoration will be used for the statistical data analysis.

6.4.2 Primary Analysis

Regarding the primary outcome, the interim analysis will be done at baseline. The final analysis of the primary outcome will be done after completion of the 1-month recall. The analysis will be done by the principal investigator within 3 months after the collection of the 1-month data.

A non-parametric test (Mann-Whitney) between two independent groups will be used to compare the level of postoperative hypersensitivity (FDI 11) between the control and the test group.

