Inclusion / exclusion criteria:	
Inclusion criteria:
 
 - Age: 18-65 years - Informed consent signed and understood by the subject - Indication for indirect restorations (inlay, onlay) in molar or premolar - replacement of insufficient fillings (e.g. due to caries at margins, filling fracture, fracture of the tooth, poor quality of the surface, leaking margin, etc.) or extensive primary caries - The occlusal area of the restoration must cover at least 1/3 of the occlusal area of the tooth. - Pre-operative discomfort of the tooth to be restored should not exceed 3 on the visual analogue scale (VAS) (0=no pain, 10=maximum conceivable pain) due to temperature stimulus or bite sensitivity - Max. 2 restorations per participant in different quadrants. - Vital tooth - Healthy periodontium, no active periodontitis - Contact with adjacent teeth (at least at one side) and opposing teeth present with at least one contact point. - Sufficient language skills 
Exclusion criteria:
 
 - Sufficient isolation not possible, dry working field cannot be guaranteed - Participants with a proven allergy to one of the ingredients of the materials used (methacrylates, HEMA, potassium iodide, mequinol) - Participants with proven allergy to local anaesthetics (Articain, sulfite) - High caries activity/ poor oral hygiene - Participants with severe systemic diseases - Pregnancy - Tooth with irreversible pulpitis - Indication for direct pulp capping - Part of the development project team of [REDACTED] - Staff of the study management team - Staff of the internal clinic - Bleaching of teeth within the last 14 days - Usage of peroxide-based disinfectants within the last 14 days

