Measurements and procedures:	
After information and written informed consent the participants will receive a dental treatment in relation to the restorative indication (caries, tooth/restoration fracture, insufficient restoration, etc), which means that the inlay/onlay cavity will be prepared and a digital impression with an intraoral scanner (Trios 3Shape) will be taken. Then, the cavities will be temporarily restored with provisional restorations. The scans will be sent to the lab where dental technicians will provide the final restorations made of lithium disilicate e.max CAD. In the following appointment the final restorations will be luted and final corrections as well as the finishing and polishing procedures will be done.
 
The baseline recall will take place 6-12 days after the insertion of the restoration. At the baseline recall the study specific parameters will be evaluated according to the FDI criteria ranging from 1 excellent to 5 clinically not acceptable.
 
Further recalls will be performed at 1, 6, 12, 24, 36 and 60 months after placement of the restoration.

Intervention:	
After getting a tooth which is in a need of a restoration (inlay or onlay), the cavity will be prepared, and an optical impression is taken. Then provisional restoration is cemented during the time, which is necessary to produce the indirect restoration in the dental lab. This first treatment appointment takes around 2.5 h. In a second treatment appointment the indirect ceramic restoration is luted to the tooth surface by the investigational product [REDACTED] and the well-established luting composite Variolink Esthetic DC. This will take at maximum 2 hours. During the baseline appointment a repolish of the restoration can be done by the operator before the evaluator assesses the restoration and the tooth. This will take at maximum 30 minutes. All following recall visits will take no longer than 30 minutes.

Control intervention (if applicable):	n.a.
Number of subjects with rationale:	45 teeth, at maximum two teeth per participant according to the statistical considerations.
Duration of the investigation:	5 years

Investigation schedule:	October 2024 First- subject –In (planned) April 2031 of Last- subject –Out (planned)

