6.1 Hypothesis

The null hypothesis is that there is a statistically significant difference between control and test group with respect to postoperative hypersensitivity.

The alternative hypothesis is that there is no difference between control and test group with regard to postoperative hypersensitivity.

We do not expect in this equivalence study to find any statistical significance between control and test group with regard to postoperative hypersensitivity.

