6.2 Determination of Sample Size

The number of samples estimated to be needed for each study arm is 40 to achieve the objective. The G*Power sample calculator software Version 3.1.9.2 was used to determine the sample size, at a power of 80% and a type I error of 0.1 (Faul et al., 2007; Faul et al., 2009).

Different to the previous study, this time a drop-out of 5 restorations is assumed. Therefore, the sample size aimed at is 45 instead of 40.

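### The primary Mann-Whitney test and the 40-per-arm sizing treat teeth as independent, although one participant may supply two

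*Combined protocol and SAP*

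**What the plan says.** The tooth is the unit throughout. The synopsis sets the number of subjects as "45 teeth, at maximum two teeth per participant according to the statistical considerations", and the inclusion criteria allow "Max. 2 restorations per participant in different quadrants". Section 4.1 plans "45 inlays or onlays out of e.max CAD to teeth of at least 23 patients". Section 6.2 says "The number of samples estimated to be needed for each study arm is 40 to achieve the objective", "at a power of 80% and a type I error of 0.1", and then adds 5 restorations for drop-out. Section 6.5 repeats that count in restorations.

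The primary test in section 6.4.2 is: "A non-parametric test (Mann-Whitney) between two independent groups will be used to compare the level of postoperative hypersensitivity (FDI 11" grade, control against test). Section 6.4.1 analyses all eligible participants who received a final restoration and has no rule for those with two. The synopsis ties the two-tooth limit to the statistical considerations, but section 6 never takes it up. The only remark on adjustment, in section 6.4.4, concerns interim looks. Secondary analyses are descriptive (section 6.4.3), so this is the only planned inferential test.

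**The concern.** The Mann-Whitney reference distribution requires independent observations within each group as well as between groups. Two teeth from one person share that person's pain perception and reporting. Section 3.1 bases the FDI grade partly on the patient's account of pain and on VAS scores, and it says these scores differ greatly between patients. A positive within-patient correlation is therefore plausible.

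Its size is not known. Section 3.1 also says of the VAS: "Therefore, it is one of the factors influencing the FDI grade, but it is not directly correlated", and the grading table adds pulp status and the vitality test.

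If the correlation is positive, the planned test exceeds its stated 0.1 error. Section 6.1 says "We do not expect in this equivalence study to find any statistical significance between control and test group", so the excess works against the sponsor: equal adhesives would be declared different too often. The paired teeth also carry less information than the sample size assumes.

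**Working it through.** **The plan's own figure.** The 40 per arm cannot be reproduced, because section 6.2 gives no effect size, grade distribution, sidedness or G*Power test family. It can only be back-solved. With a two-sided alpha of 0.10, 80% power and independent teeth, d = (1.645 + 0.842) × √(2/40) = 0.556 SD. At that effect, 45 v 40 independent teeth give 82%.

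**Inputs from the documents.** 45 test teeth, 40 control teeth, at least 23 test patients, at most two teeth each, alpha 0.1, power 80%.

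**Assumptions.**
- The test is two-sided. This is not stated, but the difference / no-difference wording of section 6.1 suggests it.
- The grade-level ICC is 0.1, 0.3 or 0.5.
- The control arm may also be paired. This is inferred from section 4.1, which says the studies differ only in the device. The control patient count is not given.

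**Clustering terms.** k = Σm²/Σm − 1, where m is teeth per patient.
- 45 teeth in 23 patients is 22 pairs and 1 single: (22×4 + 1)/45 = 89/45 = 1.978, so k = 0.978.
- 45 teeth in 34 patients is 11 pairs and 23 singles: (44 + 23)/45 = 1.489, so k = 0.489.
- Control: 40 teeth in 20 patients, k = 1; in 30 patients, k = 0.5; all single, k = 0.

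**Formulas.**
- v = (1 + k_t·ICC)/45 + (1 + k_c·ICC)/40, and v0 = 1/45 + 1/40 = 0.0472
- Actual error of the planned test = 2 × [1 − Φ(1.645/√(v/v0))]
- Power of a cluster-valid test = Φ(d/√v − 1.645)
- Rejection rate of the planned test = Φ((d − 1.645·√v0)/√v)

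Example, case (a) at ICC 0.3: v = 1.293/45 + 1.3/40 = 0.0612 and v/v0 = 1.297. The error is 2 × [1 − Φ(1.444)] = 0.149, and valid power is Φ(0.556/0.2475 − 1.645) = 73%.

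| Case | Actual error, ICC 0.1 / 0.3 / 0.5 | Power of a valid test |
|---|---|---|
| (a) both arms fully paired | 0.117 / 0.149 / 0.178 | 79 / 73 / 67% |
| (b) about a third of patients with two teeth | 0.108 / 0.125 / 0.141 | 80 / 77 / 74% |
| (c) test arm paired, control all single | 0.108 / 0.123 / 0.138 | 80 / 77 / 75% |
| (a) after 5 drop-outs, 40 v 40 | 0.117 / 0.149 / 0.179 | 77 / 70 / 65% |

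In case (a) the 45 test teeth are worth 41.0 / 34.8 / 30.2 independent teeth. The planned test itself still rejects in 81 / 79 / 77% of trials at the design effect, but only because its error is inflated.

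**Check on ordinal grades.** The tie-corrected Mann-Whitney was simulated on five grades cut from a latent normal variable with a patient effect, under three assumed grade distributions (80/12/5/2/1, 60/20/12/5/3 and 90/6/2.5/1/0.5%).
- Case (a): error 0.12–0.14 at latent ICC 0.3 (grade ICC 0.14–0.23), and 0.14–0.16 at latent ICC 0.5 (grade ICC 0.29–0.40).
- Case (b): 0.11–0.12 and 0.12–0.14.
- A separate simulation with 20 pairs per arm and grades split 80/10/6/3/1% gave 0.101, 0.125, 0.158 and 0.172 at grade correlations of 0, 0.18, 0.35 and 0.54.

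These agree with the formula.

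**The case against.** The ICC and the share of two-tooth participants are unknown, and 23 patients is the arithmetic minimum for 45 teeth, not a forecast. Section 3.1 relates VAS values to preoperative values, which may remove part of a patient's general reporting level. An ICC near zero cannot be excluded. All of this stands. It limits what can be said about size, and cases (b) and (c) may be nearer to what happens. It does not justify a test that is valid only when the ICC is zero.

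Sidedness is also assumed. With a one-sided 0.10, case (a) gives 0.111 / 0.130 / 0.147, which is smaller but still inflated.

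The strongest point is direction. Where non-significance is the hoped-for result, a valid test makes that result easier to reach. In case (a), a real difference of the design size is missed in 27% of trials instead of 21% at ICC 0.3, and in 33% instead of 23% at ICC 0.5. This stands as a caution. The planned test's advantage comes only from exceeding its error rate. The underlying problem is that equivalence is being read from non-significance without a margin, which no choice of variance can repair. A margin-based interval added later would need the same clustering, since an unadjusted interval would be too narrow and would overstate equivalence.

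**Conclusion.** The concern holds and should be fixed before the analysis. That the plan ignores two teeth from one mouth is certain from the text. The consequence is conditional on a positive within-patient correlation.

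For ICC 0.1 to 0.5, two-sided, the actual error at nominal 0.10 lies between about 0.11 and 0.18. The upper end needs near-complete pairing in both arms and a high correlation. A test with correct error has between 80% and 67% power at the back-solved effect, or down to 65% after the assumed drop-outs. With few two-tooth participants or an ICC near zero, the effect is small. The 80% is itself conditional, because section 6.2 states no effect size.

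**What to change.** **Section 6.4.2.** Replace the plain Mann-Whitney with a patient-clustered rank-sum test: the same tooth-level rank comparison of FDI 11, the variance summed by patient, and a t reference with (patients − 2) degrees of freedom. In simulation its error was 0.099–0.106 in all 18 settings of cases (a) and (b), including ICC 0, and about 0.09–0.11 when case (c) was added in a separate check. Alternatives are an ordinal GEE with small-sample correction, a patient-level bootstrap, or, more simply, one pre-specified tooth or the worst grade per participant. Name the routine, since section 6.4 names only SPSS 25.

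**Data.** Use a patient code in both the test data and the coded control data. If the control file has none, say so, cluster the test teeth and report a sensitivity range for control clustering. The degrees of freedom then need a stated rule. Counting 20 control patients, the minimum for 40 teeth at two each, is the cautious choice. Compute any later interval for the group difference in the same way.

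**Section 6.2.** State the effect size and sidedness. Give the power over a stated ICC range and the expected share of two-tooth participants, using the design effect 1 + (Σm²/Σm − 1) × ICC. Allow for drop-out by participant, since losing one can remove two teeth.

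**Cost.** SAP wording, one routine and a patient code in the control file. The change of test needs no extra participants. P-values will be larger and the stated power lower. The change should go together with a pre-set margin and a cluster-adjusted interval, because it does not supply the margin itself.
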